4.3 Interim analyses and data monitoring

4.3.1 Data monitoring committee

An independent data monitoring committee (DMC) will periodically review unblinded efficacy and safety data to assess the benefit/risk of bimekizumab in study participants with moderate to severe HS. Efficacy data summaries and individual study participant-level data listings may be provided to the DMC to put the safety review in the context of risk/benefit. Any data to be provided is specified per the DMC charter. In addition, unblinded efficacy data analysis is planned to be provided to the DMC when approximately 66% of study participants have reached the primary efficacy endpoint at Week 16. At this analysis, formal primary endpoint comparisons between each bimekizumab dose and placebo will be provided so the DMC can make an assessment regarding the futility of each dose group. However, no early stopping of a treatment group or study will be made on the basis of superior efficacy. Therefore, no alpha adjustment is planned since the efficacy analyses will only be for futility.

Measures to ensure that unblinded interim results are not disseminated beyond the DMC will be implemented. Details of futility stopping boundaries and decision rules are detailed in the DMC Charter. The details regarding the outputs to be produced and the analyses to be performed will be provided in a separate DMC SAP.

4.3.2 Interim analysis

In addition to the futility analysis described in the previous section, an unblinded interim analysis will be performed and a corresponding interim CSR may be written after the last study participant has completed the Week 48 visit, or after the last study participant has prematurely discontinued prior to reaching Week 48. The purpose of this interim analysis is to perform a comprehensive evaluation of all available double-blind data to prepare regulatory submissions for approval of the HS indication. A final analysis and updated final CSR will be prepared once all data (through to the SFU visit) have been collected.

4.4 Multicenter studies

The center-by-treatment interaction will be tested by adding center and a center-by-treatment interaction term (Section 8.2.3.11). In the model, center will be based on the original centers prior to pooling (Section 3.7). However, if the model is unable to converge due to a low number of participants at a given center, a pooling by center will be applied in order to allow the model to converge. If convergence is still not achieved, a pooling by region will be applied. If convergence still cannot be achieved, this analysis will not be performed. Detailed strategy in Section 3.7 will be applied.

4.5 Multiple comparisons/multiplicity

To control the overall type I error rate at 0.05 for the multiple comparisons in the primary and secondary efficacy endpoints, a closed testing procedure under a parallel gatekeeping framework will be applied (Sun, 2018).

[figure not shown]
Under this framework, each bimekizumab dose of [REDACTED] and [REDACTED] will be compared to placebo in the first instance at a familywise error rate of 0.025 ($\alpha/2$). Simultaneously within each dose, closed testing for the primary and secondary efficacy endpoints will be performed as follows:

1. Step 1: Test HiSCR₅₀ at significance level 0.025.
2. Steps 2 to 6 – If Step 1 is significant at 0.025 then test each secondary endpoint sequentially in the order shown in Figure 4-1, moving to the next step only if significance achieved at 0.025.
3. In the event that Step 6 is significant at 0.025 for a given dose, then Steps 1 to 6 will be repeated for the other dose using a significance level of 0.05.

The secondary efficacy variables supporting the primary efficacy variable are listed below, and will be included in the multiplicity adjustment using the analysis methods specified in Section 8.3:

1. Proportion of study participants who achieve HiSCR₇₅ at Week 16.
 - a. bimekizumab [REDACTED] vs placebo
 - b. bimekizumab [REDACTED] vs placebo
2. Proportion of study participants who experience at least 1 flare by Week 16, with flare defined as a $\geq 25\%$ increase in AN count with an absolute increase in AN count of ≥ 2 relative to Baseline.
 - a. bimekizumab [REDACTED] vs placebo
 - b. bimekizumab [REDACTED] vs placebo
3. Absolute CFB in DLQI Total Score at Week 16.
 - a. bimekizumab [REDACTED] vs placebo
 - b. bimekizumab [REDACTED] vs placebo
4. Absolute CFB in Skin Pain Score at Week 16, as assessed by the “worst skin pain” item (11-point numeric rating scale) in the HSSDD.
 - a. bimekizumab [REDACTED] vs placebo
 - b. bimekizumab [REDACTED] vs placebo
5. Skin pain response at Week 16, based on the threshold for clinically meaningful change (defined as at least a 3 point decrease from Baseline in HSSDD weekly worst skin pain score) at Week 16 among study participants with a score of ≥ 3 at Baseline.
 - a. bimekizumab [REDACTED] vs placebo
 - b. bimekizumab [REDACTED] vs placebo

Figure 4-1: Sequence of testing

AN=abscess and inflammatory nodule; DLQI=Dermatology Life Quality Index; HiSCR₅₀=a 50% reduction in the total AN count with no increase from Baseline in abscess or draining tunnel count; HiSCR₇₅=a 75% reduction in the total AN count with no increase from Baseline in abscess or draining tunnel count; HS=hidradenitis Suppurativa; [redacted]
HS skin pain response is tested among study participants with a score of ≥ 3 at Baseline.

4.6 Use of an efficacy subset of participants

A sensitivity analysis of the primary endpoint will be performed based on the FAS, the PPS, and the CFS.

4.7 Active-control studies intended to show equivalence

Not applicable.

4.8 Examination of subgroups

Subgroup analyses will be performed on the HiSCR₅₀, HiSCR₇₅, flare, and worst skin pain response endpoints by visit for the Initial Treatment Period and Maintenance Treatment Period. Additional subgroup analyses will be performed on the CFB in the worst skin pain score as measured by HSSDD and in the DLQI total score through Week 16 as described below.

Along with the tables described, there will be tables for HiSCR₅₀, HiSCR₇₅, flare, and skin pain response endpoints which display the response difference and 95% CIs between each bimekizumab dose regimen versus placebo for each of the subgroups at Week 16. Corresponding forest plots will be prepared.

The following subgroup variables will be determined using Baseline data, except for analgesic use, lesion intervention, and antibody positivity:

- Age (<40 years, 40 to <65 years, ≥65 years)
- Gender (male, female)
- Disease duration (<median, ≥median)

The median disease duration will be calculated based on all participants in the analysis set used for analysis.

- Region (North America [Canada, USA], Western Europe [France, Germany, Ireland, Italy, Spain, United Kingdom], Central/Eastern Europe [Bulgaria, Czech Republic, Hungary, Poland], Asia/Australia [Australia, Israel, Japan])
- Weight (≤100 kg, >100 kg)
- BMI (<25 kg/m², 25 to <30 kg/m², ≥30 kg/m²)
- Race (Black or African American, White, All Other Races [American Indian or Alaska Native, Asian, Native Hawaiian or Other Pacific Islander, Other/Mixed])
- Systemic antibiotic therapy at randomization (yes, no)
- Prior biologic therapy for any indication (yes, no)
- Prior biologic therapy for HS (yes, no)
- Hurley Stage at Baseline (II or III)
- Analgesic users (yes, no), separately for the Initial Treatment Period and the Maintenance Treatment Period (Section 6.4.2 specifies how participants are classified as analgesic users)
- Lesion intervention (yes, no), separately for the Initial Treatment Period and the Maintenance Treatment Period
- Antibody positivity (confirmatory assay: negative or positive; see Section 9.3.2)
- Antihistamine users during the Initial Treatment Period (yes, no) (Section 6.4.2 specifies how participants are classified as antihistamine users) (applicable only to the skin pain response endpoint)

The following subgroups for analysis on the CFB in the worst skin pain score as measured by HSSDD and in the DLQI total score will be determined based on medication use during the Initial Treatment Period:

- Antihistamines users during the Initial Treatment Period (yes, no) (Section 6.4.2 specifies how participants are classified as antihistamine users)

- Analgesics users during the Initial Treatment Period (yes, no) (Section 6.4.2 specifies how participants are classified as analgesic users)
- Systemic antibiotic therapy start/increase after randomization during the Initial Treatment Period (yes, no)

All summaries will be based on imputed data as appropriate and will include descriptive statistics only.

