6.4.2 Classification of participants as analgesic, antihistamine users

If a participant has taken a new analgesic/increased regimen of analgesic, or taken an antihistamine, on 1 or more days (need not be consecutive) in a study period (Initial Treatment Period or Maintenance Treatment Period), then for that period the participant will be classified as an analgesic or antihistamine user, respectively. The period under consideration is to match the period as defined for the HSSDD for the Initial Treatment Period or HSSQ for the Maintenance Treatment Period, based on dates/times of the medications taken.

New analgesic/increased regimen of analgesic use, regardless of indication, is defined as an analgesic medication with start date on or after the first dose of study medication. Stable

analgesics (ie, analgesics which were taken already before randomization) will not be included in this category of analgesic user. This classification will be used for selected subgroup analyses.

Antihistamine use is identified by considering the ATC classification. This classification is used for analyzing the Worst Itch endpoint and for selected subgroup analyses, by visit, for the Initial Treatment Period and Maintenance Period as applicable.

Additionally, if a participant has taken a new analgesic/increased regimen of analgesic on 1 or more days (need not be consecutive) prior to the Week 16 visit, then for that week the participant will be classified as an analgesic user. This classification will be used to adjust the formal analysis of the Worst Skin Pain secondary endpoints. If there is a visit date but no HSSDD available at the visit, then the analgesic/antihistamine user status for that week will be derived based on the visit date. If there is no visit available, then the weekly analgesic/antihistamine user status will default to the analgesic/antihistamine status for the overall study period.

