8.1 Lesion count assessment

The primary efficacy endpoint and some of the secondary and other efficacy endpoints discussed in Section 8.3 and Section 8.4 are based on the assessment and/or counts of different types of lesions in the following main anatomical regions at each visit.

- Inguinal (groin)
- Axillary (armpit)
- Chest/breast
- Gluteal
- Abdomen including supra pubic
- Back
- Head
- Neck
- Leg
- Other

These anatomical regions are further classified into the following locations, for the left and right sides of the body, as applicable:

- Inguinal excluding genital and pubic area
- Inguinal including genital and pubic area
- Submammary
- Intermammary
- Chest
- Breast
- Gluteal – Buttocks
- Gluteal – Perianal/Perineal
- Scalp
- Face

All “Other” anatomical regions with lesions present will be specified in free text on the eCRF.

The number of each of the following types of lesions will be recorded in each anatomical region, and then summed across all anatomical regions:

- Abscesses
- Inflammatory nodules
- Non-inflammatory nodules
- Draining tunnels (fistulas/sinus tracts)

- Non-draining tunnels (fistulas/sinus tracts)
- HS scars

If participants undergo lesion interventions as specified in the study protocol, the affected lesions will be counted by the Investigator as permanently present, thus accounting for potential bias due to the intervention. Section 8.4.23 specifies how the intervention data will be presented.

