8.4.23 Lesion intervention

Investigators will have the option to perform interventions in the event an acutely painful lesion occurs that requires immediate intervention.

The following rules will be used to assign a lesion intervention to a study period:

- **Initial Treatment Period:** a lesion intervention will be assigned to the Initial Treatment Period if it has been performed between the first administration of IMP on Day 1 up to and including Week 16.
- **Maintenance Treatment Period:** a lesion intervention will be assigned to the Maintenance Treatment Period if it has been performed between Week 16 through the Week 48 visit.

Methods for dealing with partial dates are specified in Section 4.2.4.

A listing of participants who receive any lesion intervention will be provided.

The number and percentage of participants who receive at least 1 lesion intervention will be summarized by treatment group for the Initial Treatment Period, Maintenance Treatment Period, and the combined Initial and Maintenance Treatment Period.

The number and percentage of participants with 2, 3, and 4 or more lesion interventions will also be summarized by treatment group for the Initial Treatment Period, Maintenance Treatment Period, and the combined Initial and Maintenance Treatment Period.

The number and percentage of participants with 2 or more lesion interventions performed on the same lesion will be summarized by treatment group for the Initial Treatment Period, Maintenance Treatment Period, and the combined Initial and Maintenance Treatment Period.

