9.3.2 Anti-bimekizumab antibodies

Anti-bimekizumab antibodies (ADAb) will be measured using a 3-tiered assay approach: screening assay, confirmatory assay, and titration assay. Samples confirmed as positive within the confirmatory assay will be further evaluated for the presence of neutralizing anti-bimekizumab antibodies specific to IL-17AA, IL-17FF or both. Samples will be taken at Baseline, then at study Weeks 4, 8, 12, 16, 20, 24, 36 and 48, and at PEOT and SFU timepoints.

ADAb samples are not analyzed when study participants are on a treatment other than bimekizumab. For study participants who switch from placebo to bimekizumab, samples are analyzed starting at the visit when the switch to bimekizumab occurs (Week 16). The sample at Week 16 will act as the Baseline for that treatment group.

The screening cut point will be used to determine the status of anti-bimekizumab antibodies in the test sample as Positive Screen (PS) or Negative Screen (NS). For samples presenting anti-bimekizumab antibody levels that are PS, a further confirmatory assay will be performed, and the result of which will be reported as either Positive Immunodepletion (PI) or Negative Immunodepletion (NI).

ADAb status for each sample will be derived as follows:

- Sample values that are either NS, or PS and NI and where the bimekizumab concentration is less than the validated ADAb assay drug tolerance limit will be defined as anti-bimekizumab antibody negative.
- Sample values that are either NS, or PS and NI and where the bimekizumab concentration exceeds the validated ADAb assay drug tolerance limit will be defined as inconclusive.

- Sample values that are PS and PI will be defined as ADAb positive (regardless of availability of a titer value)
- Missing or non-evaluable samples will be defined as missing

Positive immunodepletion samples will be titrated, and the ADAb titer (reciprocal dilution factor including minimum required dilution) will be reported. Subsequently, PI samples will also be subject to a neutralizing assay to evaluate the potential of ADAb to neutralize the target binding of bimekizumab (IL-17AA or IL-17FF or both) in vitro.

Cumulative ADAb status will be derived as follows:

The ADAb status (positive, negative or missing) will be considered in a cumulative manner at each time point.

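### Week 16 differences versus placebo are planned within subgroups set after randomization; for antibody status the contrast cannot be interpreted, and for analgesic, lesion-intervention and antihistamine use it is not protected by randomization

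*SAP*

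**What the plan says.** SAP Section 4.8 covers four binary endpoints: HiSCR50, HiSCR75, flare and skin pain response. For these it plans tables that "display the response difference and 95% CIs between each bimekizumab dose regimen versus placebo for each of the subgroups at Week 16", and adds: "Corresponding forest plots will be prepared". No subgroup is excused from the placebo contrast.

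The section takes its subgroup variables from Baseline data "except for analgesic use, lesion intervention, and antibody positivity". The same list ends with antihistamine use during the Initial Treatment Period (skin pain response only), which is also not a Baseline variable but is missing from that exception. The section closes by limiting the summaries to descriptive statistics.

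The definitions are elsewhere in the SAP:

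- **Antibody status (Section 9.3.2).** "ADAb samples are not analyzed when study participants are on a treatment other than bimekizumab". For the placebo arm, analysis starts at the Week 16 switch, and that sample serves as the arm's Baseline. The efficacy-subgroup rule calls a participant positive after at least 2 positive on-treatment time points, not counting Baseline or follow-up. It also has negative and missing groups.
- **Analgesic use (Section 6.4.2).** An "analgesic medication with start date on or after the first dose of study medication", whatever the reason for taking it.
- **Lesion intervention (Section 8.4.23).** Assigned to the Initial Treatment Period if "performed between the first administration of IMP on Day 1 up to and including Week 16". Under Section 8.1, "the affected lesions will be counted by the Investigator as permanently present".

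**The concern.** A subgroup contrast with placebo can be read causally only if membership is fixed before treatment can influence it. Section 4.8 recognizes that some of its variables are not, but gives them the same display as age, sex or Hurley Stage. In a forest plot these rows would stand beside genuine Baseline subgroups and be read in the same way.

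Two problems follow. For antibody status, the placebo side of the contrast is empty or is defined by something that happens after the outcome. For the other variables, treatment may change who enters each stratum, so a difference within a stratum need not reflect a treatment effect there.

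**Working it through.** **Antibody status.** Section 9.3.2 schedules samples at Baseline and Weeks 4, 8, 12, 16, 20, 24, 36 and 48, plus premature end of treatment and safety follow-up. Countable on-treatment samples by Week 16 are:

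- Bimekizumab arms: Weeks 4, 8, 12 and 16, so up to 4.
- Placebo arm: the samples up to Week 12 are not analyzed and Week 16 is the arm's Baseline, so 0.

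The rule needs at least 2 positives. With 0 countable samples, no placebo participant can be positive by Week 16 and the positive row has no comparator. On scheduled visits, the earliest a placebo-arm participant can have 2 on-treatment samples is Week 24 (Weeks 20 and 24). That is 8 weeks after the outcome and depends on bimekizumab exposure. Participants who leave the placebo arm before the switch have no analyzed sample.

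Section 9.3.2 says these efficacy categories can also be used, and Section 4.8 does not name the rule or the period. If the overall-status rule (at least one positive sample) were used instead, a placebo participant could be positive on the Week 16 sample alone. That reflects reactivity before any bimekizumab and would be set against antibodies arising on treatment, which is still not a like-for-like contrast.

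**Analgesic use, lesion intervention, antihistamine use.** All three are recorded after first dose. Lesion intervention has a further link: a treated lesion stays in the count, so the variable that defines the subgroup directly affects HiSCR50, HiSCR75 and flare.

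**How large a bias could be.** The plan states no figure for this and gives no use rates by arm, so only an illustration with assumed parameters is possible. Response rates come from Table 2-1: HiSCR50 of 0.50 (N=140) versus 0.25 (N=70). As a check on these inputs, the stated power of 0.90 at two-sided 0.025 reproduces:

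- pooled rate = (70 × 0.25 + 140 × 0.50)/210 = 0.4167
- SE under the null = √[0.4167 × 0.5833 × (1/70 + 1/140)] = 0.0722
- SE under the alternative = √[0.1875/70 + 0.25/140] = 0.0668
- power = Φ[(0.25 − 2.241 × 0.0722)/0.0668] = 0.907

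The assumed model has latent severity U ~ N(0,1), logit(response) = a − gU and logit(use) = b + gU, with a and b set in each arm to give the stated rates, and g = 1 or 2. Entries are bimekizumab minus placebo, users / non-users.

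| Use, placebo v bimekizumab | g | No true effect (0.25 v 0.25) | Table 2-1 rates (0.50 v 0.25) |
|---|---|---|---|
| 20% v 20% | 1 | 0.000 / 0.000 | 0.207 / 0.261 |
| 20% v 20% | 2 | 0.000 / 0.000 | 0.130 / 0.280 |
| 30% v 15% | 1 | −0.018 / −0.019 | 0.185 / 0.239 |
| 30% v 15% | 2 | −0.023 / −0.042 | 0.093 / 0.231 |
| 50% v 10% | 1 | −0.046 / −0.054 | 0.150 / 0.202 |
| 50% v 10% | 2 | −0.065 / −0.125 | 0.035 / 0.142 |

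The no-effect column isolates what the split does. It is zero when use is equal across arms and grows as use diverges. Under no effect the arms are interchangeable, so reversing the use rates (more use on bimekizumab) reverses the signs. At 50% v 10% with the Table 2-1 rates, both strata fall below the overall difference of 0.25. The last column also contains ordinary scale dependence, as its 20% v 20% rows show, so it should not be read as bias alone.

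**The case against.** The strongest reply is that these displays are exploratory. They carry no p-values or interaction tests, lie outside the testing procedure of Section 4.5, do not appear among the nominal tests of Section 8.5, and are called descriptive. Section 4.8 also says openly that three of the variables are not Baseline-determined. All of that is true and limits the consequence. It does not make the contrasts interpretable: a between-arm difference with a 95% CI in a forest plot is a comparison with placebo, whatever its label.

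Three stronger readings are tempting but not supported.

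- **That placebo has no antibody classification at all.** It does have an analyzed Week 16 sample, and Section 9.3.2 provides negative and missing groups. What is lacking is any on-treatment status by Week 16.
- **That the other contrasts are biased, because analgesic use and intervention result from poor disease control.** Section 6.4.2 counts analgesics regardless of indication; only lesion intervention is tied, in Section 8.4.23, to an acutely painful lesion. With equal use in both arms, the illustration shows no spurious difference under no effect. The supportable statement is that they can be biased.
- **That the split alone must create an interaction.** Suppose 20% of responders and 50% of nonresponders use analgesics in both arms, with response 0.50 v 0.25. The differences are 0.10/0.35 − 0.05/0.425 = 0.168 in users and 0.40/0.65 − 0.20/0.575 = 0.268 in non-users. But the odds ratio is (0.10/0.25)/(0.05/0.375) = 3.0 in users, (0.40/0.25)/(0.20/0.375) = 3.0 in non-users, and (0.50/0.50)/(0.25/0.75) = 3.0 overall. The 10-point gap is scale dependence, which a purely prognostic Baseline factor would also show, so it is not evidence of bias.

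**Conclusion.** The point stands in two parts of different strength.

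For antibody status it follows from the SAP's own text and needs no assumed numbers. Under the efficacy-subgroup rule the positive row has no placebo comparator by Week 16, and the alternatives rest on post-outcome bimekizumab exposure or on a pre-exposure sample.

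For analgesic use, lesion intervention and antihistamine use, the placebo contrasts are not protected by randomization and can be biased. Size and direction cannot be settled from the SAP. The range of 0 to about 13 points under no true effect rests wholly on the assumed severity model and use rates.

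The omission of antihistamine use from the exception sentence is a plain inconsistency within Section 4.8. None of this affects the primary, secondary or multiplicity-controlled results. It is worth correcting because the affected rows could be misread and the correction is nearly free.

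**What to change.** In Section 4.8:

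1. Limit the Week 16 placebo-difference tables and forest plots to subgroups defined at Baseline.
2. Present antibody status for the bimekizumab arms only, and state which Section 9.3.2 rule and which period define it.
3. Present the analgesic, lesion-intervention and antihistamine subgroups as response rates within each arm, without a treatment difference.
4. Add antihistamine use to the sentence listing variables not set at Baseline.

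The cost is a change of SAP wording and a few fewer exploratory forest-plot rows. No new data are needed.
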